1.2.3.1. Phase 1 Safety and Pharmacokinetics

Study GS-US-141-1218 was a four part, first-in-human study. Parts A and B were randomized, double-blind, placebo-controlled, single and multiple ascending dose studies of GS-9883 in healthy male and female subjects. Part C was an open label, fixed sequence food effect study evaluating the effect of food on the PK of GS-9883. Part D was a randomized, open-label, 2-cohort, 3-period, crossover PK study evaluating the drug interaction potential between FTC/TAF FDC tablet and GS-9883 in healthy subjects.

There was no difference in the overall incidence or type of AEs when GS-9883 was administered in the fasted and fed states. There was no difference in the overall incidence of AEs when GS-9883 or FTC/TAF was each administered alone or in combination.

No deaths or pregnancies were reported. No Grade 3 or 4 AEs or SAEs, were reported in any cohort.

Changes in serum creatinine were observed in this study, presumably via inhibition of the renal transporter OCT2. In the MAD cohorts (fasted), serum creatinine change at Day 14 ranged from 0.05 mg/dL for the 5 mg cohort to 0.18 mg/dL for the 300 mg/dL cohort. In Part D (DDI), conducted in the fed state (regular meal), subjects received 100 mg GS-9883 monotherapy for 7 days and 100 mg GS-9883 with FTC/TAF for 7 days, the mean serum creatinine change at Day 7 was 0.14 mg/dL following GS-9883 and 0.17 mg/dL following GS-9883 + FTC/TAF. All changes returned to baseline after discontinuation of GS-9883.

The majority of laboratory abnormalities were Grade 1 or Grade 2 in severity. Grade 3 laboratory abnormalities included 10 subjects with Grade 3 urine dipstick tests for blood. All of these subjects were female, none of the labs were considered by the Investigator to be clinically significant, and all were associated with menstruation. No other Grade 3 or 4 laboratory abnormalities were observed.

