Study Days are calculated relative to Study Day 1 for either the randomized phase analysis or the all B/F/TAF analysis, as appropriate. For events that occurred on or after the Study Day 1 date of either analysis, study days are calculated as (visit date minus the date of Study Day 1 plus 1). For events that occurred prior to Study Day 1 for either analysis, study days are calculated as (visit date minus the date of Study Day 1).

Last Study Date is the latest of the study drug (including B/F/TAF and DTG/F/TAF in both phases) start dates and end dates, the clinic visit dates, and the laboratory visit dates, including the 30-day follow-up visit date.

Baseline Value is defined as the last nonmissing value obtained on or prior to Study Day 1 for either the randomized phase analysis or the all B/F/TAF analysis, as appropriate. Subjects who actually received DTG+F/TAF in the randomized phase and received at least 1 dose of B/F/TAF in extension phase will have a new baseline value for the All B/F/TAF analysis.

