Battery	Lab Test Label Used in I-labtox Listing	Toxicity Direction	Lab Test Label Used in t-labtox Table
	Corrected Calcium	Increase	Corrected Calcium (Hypercalcemia)
	Corrected Calcium	Decrease	Corrected Calcium (Hypocalcemia)
	Creatine Kinase (CK)	Increase	Creatine Kinase (Increased)
	Creatinine	Increase	Creatinine (Increased)
	GGT	Increase	GGT (Increased)
	Lipase	Increase	Lipase (Increased)
	Magnesium	Decrease	Magnesium (Hypomagnesemia)
	Phosphate	Decrease	Phosphate (Hypophosphatemia)
	Serum Glucose (Fasting)	Increase	Serum Glucose (Fasting, Hyperglycemia)
	Serum Glucose (Fasting)	Decrease	Serum Glucose (Fasting, Hypoglycemia)
	Serum Glucose (Nonfasting)	Increase	Serum Glucose (Nonfasting, Hyperglycemia)
	Serum Glucose (Nonfasting)	Decrease	Serum Glucose (Nonfasting, Hypoglycemia)
	Serum Potassium	Increase	Serum Potassium (Hyperkalemia)
	Serum Potassium	Decrease	Serum Potassium (Hypokalemia)
	Serum Sodium	Increase	Serum Sodium (Hypernatremia)
	Serum Sodium	Decrease	Serum Sodium (Hyponatremia)
	Total Bilirubin	Increase	Total Bilirubin (Hyperbilirubinemia)
	Total Cholesterol (Fasting)	Increase	Total Cholesterol (Fasting, Hypercholesterolemia)
	Triglycerides (Fasting)	Increase	Triglycerides (Fasting, Increased)
	LDL (Fasting)	Increase	LDL (Fasting, Increased)
Urea Nitrogen (BUN)	Increase	Urea Nitrogen (Increased)	
Uric Acid	Increase	Uric Acid (Hyperuricemia)	
Uric Acid	Decrease	Uric Acid (Hypouricemia)	
Urinalysis	Urine Blood (Dipstick)	Increase	Urine RBC (Hematuria, Quantitative or Dipstick)*
	Urine Glucose	Increase	Urine Glucose (Glycosuria)
	Urine Protein	Increase	Urine Protein (Proteinuria)
	Urine RBC (Quantitative)	Increase	Urine RBC (Hematuria, Quantitative or Dipstick)*

* Due to the reflexive nature of the quantitative urine RBC test, results will be combined with the dipstick test of urine blood as described below. General rule is that urine RBC (Quantitative) should always be used first (if available), no matter it is collected at the same time of Urine Blood (Dipstick) or not. The combined Urine RBC (hematuria, Quantitative or Dipstick) toxicity grade will be used for “Maximum treatment-emergent toxicity grade” summary.

Is Post-BL Urine RBC (Quant.) Result Available?	Is BL Urine RBC (Quant.) Result Available?	Is Post-BL Urine Blood (Dipstick) Result Available?	Is BL Urine Blood (Dipstick) Result Available?	How to Determine Treatment-Emergent Toxicity for “Urine RBC (Hematuria, Quantitative or Dipstick)”

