Yes	Yes	-	-	Compare post-BL Urine RBC (Quant.) toxicity grade to BL Urine RBC (Quant.) toxicity grade. If post-BL toxicity is greater than BL toxicity, then treatment-emergent
Yes	No	-	-	Treatment-emergent. Use post-BL Urine RBC (Quant.) toxicity grade.
No	-	Yes	Yes	Compare post-BL Urine Blood (Dipstick) toxicity grade to BL Urine Blood (Dipstick) toxicity grade. If post-BL toxicity is greater than BL toxicity, then treatment-emergent
No	-	Yes	No	Treatment-emergent. Use post-BL Urine Blood (Dipstick) toxicity grade.
No	-	No	-	Do not count subject in the denominator for “Urine RBC (Hematuria, Quantitative or Dipstick)”

BL = Baseline. Quant = Quantitative. “-” means any value can be present (or it can be missing), as it does not affect the classification

16) Concomitant nonstudy-drug ARV medications for all B/F/TAF analysis (ie, ARV medications other than study drug that are taken while receiving study drug B/F/TAF) will be flagged in “Nonstudy-Drug Antiviral Medication” listing. The logic to define concomitant nonstudy-drug ARV is similar to concomitant non-ARV Medications (see details in Section 7.4.2)

17) Lipid modifying medication analyses for All B/F/TAF analysis:

Lipid modifying medication is defined to be the concomitant medication with ATC2 term = “LIPID MODIFYING AGENTS” and CMDECOD contains wording of “STATIN” in the ADCM dataset.

Subjects who took lipid-modifying medications at the first dose of B/F/TAF (including both phases) refer to the subjects who use of the lipid-modifying agents at study day 1 of all B/F/TAF analysis. More specifically, subjects with “Lipid Modifying Agent Use at the first dose of B/F/TAF” include those subjects in All B/F/TAF Analysis Set with: 1) any selected CM record with the start date ≤ the first dose date of B/F/TAF (including both phases), and 2) the end date of the selected CM record is ongoing or the end date of the selected CM record ≥ the first dose date of B/F/TAF (including both phases).

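### When a post-baseline quantitative urine RBC exists, the haematuria rule can set an old reflex result above a later negative pre-dose dipstick, or ignore a positive baseline dipstick

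*SAP*

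**What the plan says.** SAP Appendix 6 item 15 reports haematuria as one combined parameter from two tests and describes the quantitative RBC as reflexive. It sets this order of precedence: "urine RBC (Quantitative) should always be used first (if available), no matter it is collected at the same time of Urine Blood (Dipstick) or not". A five-row table then sets treatment-emergent status:

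- Row 1, quantitative result present both post-baseline and at baseline: "Compare post-BL Urine RBC (Quant.) toxicity grade to BL Urine RBC (Quant.) toxicity grade".
- Row 2, quantitative result present post-baseline but not at baseline: "Treatment-emergent. Use post-BL Urine RBC (Quant.) toxicity grade".
- Row 3, no post-baseline quantitative result, dipstick present at both times: "Compare post-BL Urine Blood (Dipstick) toxicity grade to BL Urine Blood (Dipstick) toxicity grade".
- Row 4, no post-baseline quantitative result and no baseline dipstick: the post-baseline dipstick is emergent.
- Row 5, neither test post-baseline: the subject leaves the denominator.

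Both dipstick columns hold a dash in rows 1 and 2. The table note says a dash "means any value can be present (or it can be missing), as it does not affect the classification".

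On baseline, SAP Section 3.8.1 states: "Baseline Value is defined as the last nonmissing value obtained on or prior to Study Day 1". Appendix 6 item 13 applies the same idea to toxicity grades, anchored on the first B/F/TAF dose. Neither place sets a look-back limit. Section 3.8.1 also gives subjects who switch from DTG+F/TAF a new baseline at their first extension dose.

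**The concern.** A reflex test exists for only some urine samples, whereas urinalysis is scheduled at every visit, including the End of Blinded Treatment Visit, when open-label drug is dispensed (Protocol Section 6.5.2 and Appendix 2). The most recent quantitative result and the most recent urinalysis can therefore be far apart in time. Rows 1 and 2 look only at the former.

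Two errors can follow. Under row 1, an old and possibly transient grade can stand as baseline although the last pre-dose dipstick was negative, and haematuria that is new on B/F/TAF then fails to exceed it. Under row 2, haematuria already visible on the baseline dipstick can be counted as new because no quantitative result was reported then. At stake is the treatment-emergent haematuria line in the final laboratory-abnormality tables, and whether its two columns use comparable baselines.

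**Working it through.** There is no plan figure to reproduce, because this is a classification rule. The check runs the possible inputs through the table.

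**Which rows are affected.** Each of four results (post-baseline quantitative, baseline quantitative, post-baseline dipstick, baseline dipstick) is present or absent, giving 2^4 = 16 patterns. Rows 1 to 4 take 4, 4, 2 and 2 of these, so 12 are countable. Row 5 excludes the other 4.

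- A baseline quantitative result exists in 6 countable patterns. It serves as baseline in 4 (row 1) and is ignored in 2 (one each in rows 3 and 4).
- A baseline dipstick exists without a baseline quantitative result in 3 countable patterns. It is ignored in 2 (row 2) and used in 1 (row 3).

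The problem is thus confined to rows 1 and 2, which require a post-baseline quantitative result.

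**How old the row 1 comparator can be.**

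- DTG+F/TAF to B/F/TAF group: blinded treatment lasts at least 144 weeks (SAP Section 1.2), and 144 × 7 = 1008 days, or 1008 / 365.25 = 2.76 years. A screening sample taken up to 30 days before Day 1 (Protocol Section 6.2.1) gives (1008 + 30) / 365.25 = 2.84 years. Before the End of Blinded Treatment Visit there are at least 16 scheduled urinalyses: screening, Day 1 and 14 visits from Week 4 to Week 144. The latest quantitative result could come from any of them.
- Randomized B/F/TAF group: only screening and Day 1 precede the first dose, so the comparator is at most about 30 days old.

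**What row 1 can miss.** Protocol Appendix 5 grades haematuria 1 to 3 on each test. Suppose the last pre-dose dipstick was negative (Grade 0), an older quantitative result was Grade 1 to 3, and a post-baseline quantitative result is Grade 1 to 3. That gives 3 × 3 = 9 combinations. Against the last pre-dose urinalysis all 9 are emergent. Row 1 flags only those where the new grade exceeds the old one: (2,1), (3,1) and (3,2). It misses 9 − 3 = 6. If the old quantitative result was Grade 0, row 1 misses nothing.

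**What row 2 can over-call.** Take a post-baseline quantitative Grade 1 to 3 with a baseline dipstick Grade 0 to 3 and no baseline quantitative result: 3 × 4 = 12 combinations. Row 2 flags all 12. Comparison with the baseline dipstick would flag those where the new grade is higher: 1 + 2 + 3 = 6. The other 6 have a baseline dipstick grade at or above the later one.

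The 6 of 9 and 6 of 12 are counts of logical combinations, not patient frequencies.

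**The case against.** The strongest reply has four parts.

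**Row 2 is the SAP's ordinary convention.** Section 7.2.2.1 counts any Grade 1 or higher result as emergent when the relevant baseline is missing. If a positive dipstick triggers the reflex, no baseline quantitative result usually means a negative baseline dipstick, and row 2 is then right. This largely stands. Row 2 errs only when a positive dipstick has no graded quantitative result. Protocol Appendix 5 leaves that open, since it assigns quantitative grades for one named laboratory only. Even so, the SAP reports one combined parameter, and for that parameter a baseline with a dipstick is not missing.

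**The undated baseline is SAP-wide.** It governs every laboratory test. True, but it does little harm for a test done at every visit. It matters for a reflex test that is given precedence over a scheduled one regardless of collection time.

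**Like should be compared with like.** Dipstick and quantitative grades share labels, but the documents do not show that they are equivalent. This stands as a cost of the fix, not as a defence of the rule: item 15 already pools both tests into one grade, and a negative pre-dose dipstick is simply Grade 0.

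**The consequence is small.** SAP Section 7.2 plans no formal laboratory testing, Section 3 plans no between-group comparison in the All B/F/TAF analysis, and by-subject urinalysis listings cover both phases. All of this stands.

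A reader might also infer that the rule always prefers a quantitative baseline and always disregards the dipstick. Rows 3 and 4 show otherwise.

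**Conclusion.** The point holds in limited form. Where a post-baseline quantitative result exists, row 1 can hide new haematuria in the DTG+F/TAF to B/F/TAF group by using a comparator that may be 1008 or more days old in place of a later negative dipstick. Row 2 can count pre-existing dipstick haematuria as new in either group, probably rarely. Row 1 is the main fault. Calling row 2 rare assumes that the reflex follows a positive dipstick, which neither document states.

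Three stronger readings are not supported:

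- **Years-old baselines throughout.** This can arise only in the switch group, because the screening window limits the other group.
- **A table biased mainly downward in the switch group.** Row 1 can under-count and row 2 can over-count, and nothing in the documents weighs one against the other.
- **A percentage of subjects affected.** That would need a reflex rate, which is not given, and independence between visits. Independence is doubtful. The Phase 1 summary in Protocol Section 1.2.3.1 reports 10 subjects with Grade 3 dipstick blood and says "All of these subjects were female, none of the labs were considered by the Investigator to be clinically significant, and all were associated with menstruation". Those were healthy volunteers, so this is background only, but it suggests that positive results may cluster within subjects.

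The effect is confined to one descriptive safety line. The primary endpoint is untouched. This is a worthwhile tidy-up, not a threat to the trial's conclusions.

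**What to change.** Rewrite the baseline part of Appendix 6 item 15 as follows:

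1. Set the baseline haematuria grade from the last urinalysis on or before the first B/F/TAF dose. Use the quantitative grade if one was reported for that sample, otherwise its dipstick grade, with a negative dipstick as Grade 0.
2. Form the post-baseline grade in the same combined way, and call it emergent only if it exceeds the baseline grade.
3. Keep emergence by default only where neither baseline result exists.

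Same-sample matching is already used elsewhere in the SAP: item 19 requires the tests that define incident coinfection to share an accession number.

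The cost is one programming rule on data already held. The downside is that some comparisons will cross methods, so a change of test alone could create or hide an emergent grade. Flag those records in the listing. The SAP carries final signatures, so any change belongs in the clinical study report, as SAP Section 1 provides for changes after finalization.

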 - Metabolic assessments: Fasting (no food or drinks, except water, at least 8 hours prior to blood collection) glucose and lipid panel (total cholesterol, HDL, direct LDL, and triglycerides). If the subject has not fasted prior to the visit, the visit may proceed, but the subject must return within 72 hours in a fasted state to draw blood for the metabolic assessments. **(Weeks 12, 24, 48, 72, 96, 120, and 144)**
 - Estimated glomerular filtration rate according to the Cockcroft-Gault formula
 - Hematology profile: complete blood count (CBC) with differential and platelet count
 - Plasma HIV-1 RNA
 - CD4+ cell count
 - Plasma storage sample for safety, virology, or PK testing
 - For subjects who meet the definition of HBV infection at any visit
 - The following will be conducted by the central laboratory: HBsAb, HBsAg (qualitative and quantitative) and HBeAg (if negative, reflex HBeAb) **(Weeks 12, 24, 48, 72, 96 and every 24 weeks post Week 96)**
 - Plasma HBV DNA

- For subjects who do NOT meet the definition of HBV infection at any visit
 - The following will be conducted by the central laboratory: Hepatitis B surface antibody (HBsAb), Hepatitis B virus core antibody (HBcAb), and Hepatitis B virus surface antigen serology (HBsAg). Subjects who are HBsAg and/or HBcAb positive will have a reflex test for HBV DNA (viral load) (**Weeks 48, 96 and 144**)
- Hepatitis C virus (HCVAb) serology. Subjects who are HCVAb positive will have a HCV RNA test performed (**Weeks 48, 96 and 144**)
- Pharmacokinetic Blood Collection for subjects who are on study drug. Details of pharmacokinetic blood sampling procedures and sample management will be documented in the Pharmacokinetic Sample Collection, Processing, Storage, and Shipment Manual.
 - **Single Anytime, Trough and Post Dose PK Samples for all subjects on study drug:**
 - Subjects will have a single anytime pre or post-dose PK blood at **Weeks 8, 24 and 36**.

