 - Chemistry profile: alkaline phosphatase, AST, ALT, GGT, total bilirubin, direct and indirect bilirubin, total protein, albumin, LDH, CPK, bicarbonate, BUN, calcium, chloride, creatinine, phosphorus, magnesium, potassium, sodium, uric acid, and amylase (reflex lipase testing is performed in subjects with total amylase $> 1.5 \times$ ULN), and TSH
 - Metabolic assessments: Fasting (no food or drinks, except water, at least 8 hours prior to blood collection) glucose and lipid panel (total cholesterol, HDL, direct LDL, and triglycerides). If the subject has not fasted prior to the visit, the visit may proceed, but the subject must return within 72 hours in a fasted state to draw blood for the metabolic assessments.
 - Estimated glomerular filtration rate according to the Cockcroft-Gault formula
 - Hematology profile: complete blood count (CBC) with differential and platelet count
 - Plasma HIV-1 RNA
 - CD4+ cell count
 - Plasma storage sample for safety, virology, or PK testing
 - Plasma HBV DNA (for subjects who meet the definition of HBV infection)
- Document study drug dispensation, if applicable, and accountability for all study drugs dispensed
- Subjects who wish to continue in the Open-Label Rollover extension study will receive open label GS-9883/F/TAF.

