Subjects will be treated for at least 144 weeks during the blinded treatment phase. After Week 144, all subjects will continue to take their blinded study drug and attend visits every 12 weeks until the End of Blinded Treatment Visit. Once the last subject completes the Week 144 visit and Gilead Sciences Inc. (Gilead) completes the Week 144 analysis, all subjects will return to the clinic (preferably within 30 days) for an End of Blinded Treatment Visit. At the End of Blinded Treatment Visit, subjects will be given the option to receive B/F/TAF FDC in an open-label (OL) extension phase for 96 weeks. After Week 96 OL, subjects will discontinue the study drug, transition onto commercially available treatment and complete a 30-Day Follow-up Visit. In a country where B/F/TAF is not available, subjects will be given the option to continue OL B/F/TAF until the product becomes accessible to subjects through an access program, or until Gilead elects to discontinue the study in that country, whichever occurs first.

All subjects participating in the OL extension phase, without regard to their blinded treatment regimen, will return for study visits at Week 12 OL and every 12 weeks thereafter for 96 weeks.

Subjects who complete the study through the End of Blinded Treatment Visit and do not continue on the OL B/F/TAF FDC extension phase will be required to return to the clinic after the End of Blinded Treatment Visit for a 30-Day Follow-Up Visit.

Treatment assignments will be provided to the investigators within 30 days of the last subject completing the End of Blinded Treatment Visit.

Schedule of Assessments

After screening procedures, eligible subjects will be randomized 1:1 to Treatment Group 1 or Treatment Group 2 and treated for 144 weeks. Following the Day 1 visit, subjects will be required to return for study visits at Weeks 4, 8, and 12, and then every 12 weeks from Week 12 through Week 144. After Week 144, all subjects will continue to take their blinded study drugs and attend study visits every 12 weeks until the End of Blinded Treatment Visit. All subjects participating in the OL extension phase, without regard to their blinded treatment regimen, will return for study visits at Week 12 OL and every 12 weeks thereafter for at least 96 weeks.

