3.8. Analysis Windows

3.8.1. Definition of Study Day

Study Day 1 for the Randomized Phase analysis is defined as the day when the first dose of study drug (ie, B/F/TAF, DTG /F/TAF) was taken, as recorded on “Randomized Phase” the Study Drug Administration eCRF form.

Last Dose Date for the Randomized Phase analysis is the latest of the randomized study drug (including B/F/TAF or DTG/F/TAF) end dates recorded on the Study Drug Administration eCRF form.

If last dose date for the Randomized Phase analysis is missing (eg, only year of last dose date is known or completely missing due to lost to follow-up), the latest of the randomized study drug start dates and end dates or the latest clinical and laboratory visit dates prior to the first dose date of B/F/TAF in the extension phase (if applicable), excluding the 30-day follow-up visit date, will be used to impute the last dose date. For other partial missing last dose date, please see the programming specifications for imputation rule details.

Study Day 1 for the all B/F/TAF analysis is defined as

- For subjects who actually received B/F/TAF in the randomized phase of this study (ie, B/F/TAF group), Study Day 1 for the all B/F/TAF analysis is defined as the day when the first dose of B/F/TAF in the randomized phase was taken, as recorded on the Study Drug Administration eCRF form.
- For subjects who actually received DTG/F/TAF in the randomized phase of this study and then receive at least 1 dose of B/F/TAF in the extension phase (ie, DTG/F/TAF to B/F/TAF group), Study Day 1 for the all B/F/TAF analysis is defined as the day when the first dose of B/F/TAF in the extension phase was taken, as recorded on the Study Drug Administration eCRF form.

Last Dose Date for the All B/F/TAF Analysis is the latest of B/F/TAF (including both phases) end dates recorded on the Study Drug Administration eCRF form.

If the last dose date for the all B/F/TAF analysis is missing (eg, only year of last dose date is known or completely missing due to lost to follow-up), the latest of the B/F/TAF (including both phases) start dates and end dates, the latest clinical and laboratory visit dates, excluding the 30-day follow-up visit date, will be used to impute the last dose date.

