5.2. Baseline Disease Characteristics

The following baseline disease characteristics will be summarized by treatment group and overall using descriptive statistics for subjects in All B/F/TAF A:

- HIV-1 RNA (\log_{10} copies/mL)
- HIV-1 RNA categories (copies/mL): (a) $\leq 100,000$, (b) $> 100,000$ to $\leq 400,000$, and (c) $> 400,000$
- CD4+ cell count (/ μ L)
- CD4+ cell count categories (/ μ L): (a) < 50 , (b) ≥ 50 to < 200 , (c) ≥ 200 to < 350 , (d) ≥ 350 to < 500 , and (e) ≥ 500
- CD4 percentage (%)
- Mode of infection (HIV risk factors)
- HIV disease status
- eGFR_{CG} (mL/min)
- HIV/HBV coinfection status (Yes/No/Missing, see Section 9.1 for definition)
- HIV/HCV coinfection status (Yes/No/Missing, see Section 9.2 for definition)

No statistical comparisons will be made for the all B/F/TAF analysis.

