9.1. Analyses for HIV/HBV Coinfected Subjects

For all B/F/TAF analyses, subjects with HIV/HBV coinfection at baseline (ie. at the first dose of B/F/TAF) are defined as subjects who meet any of the following two criteria:

- Positive HBsAg on or prior to the first dose date of B/F/TAF (including both phases), or
- Negative HBsAg, negative HBsAb, positive HBcAb, and quantifiable HBV DNA (ie, HBV DNA \geq 20 IU/mL) on or prior to the first dose date of B/F/TAF (including both phases).

The following listings will be provided for subjects with HIV/HBV coinfection at baseline:

- Listing of adverse events
- Listing of liver-related laboratory tests and HBV DNA results

Subjects with incident HIV/HBV coinfection while on study drug (if any) are defined as subjects who are not HIV/HBV coinfecting at baseline for all B/F/TAF analyses and meet any of the following criteria:

- Positive HBsAg after the first dose date of B/F/TAF (including both phases) and on or prior to the date of permanent discontinuation of B/F/TAF (including both phases), or
- Negative HBsAg, negative HBsAb, positive HBcAb, and quantifiable HBV DNA (ie, HBV DNA \geq 20 IU/mL) after the first dose date of B/F/TAF (including both phases) and on or prior to the date of permanent discontinuation of B/F/TAF (including both phases), or
- Experience any of the following adverse events (ie, selected MedDRA PTs from the SMQ of “Liver Infections”) after the first dose date of B/F/TAF (including both phases) and on or prior to the date of permanent discontinuation of B/F/TAF (including both phases): Acute hepatitis B, Chronic hepatitis B, Congenital hepatitis B infection, Hepatitis B, Hepatitis B core antibody positive, Hepatitis B DNA assay positive, Hepatitis B surface antigen positive, Hepatitis B virus test positive.

The following listings will be provided for subjects with incident HIV/HBV coinfection while on B/F/TAF (if any):

- Listing of adverse events
- Listing of liver-related laboratory tests and HBV DNA results

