- For baseline coinfection, for all B/F/TAF analysis, the baseline would be adjusted based on the first dose of B/F/TAF (including both phases), when considering the different laboratory tests, take the latest, non-missing record on or prior to the first dose date of B/F/TAF (including both phases) for each test (eg, HBsAg, HBsAb, HBcAb, and HBV DNA).
 - The baseline coinfection status will be one of the three values: Yes/No/Null
 - The following tables provide combinations of HBV and HCV tests and the corresponding baseline coinfection status

HBsAg	HBsAb	HBcAb	HBV DNA	Coinfection Status	
Positive	-	-	-	Y	
Negative	Positive	-	-	N	
	Negative	Positive	Quantifiable	Y	
			Not Quantifiable	N	
			Missing	Null	
		Negative	-	N	
		Missing	Missing	Quantifiable	Null
				Not Quantifiable	N
	Missing			Null	
	Missing	Positive	Quantifiable	Null	
			Not Quantifiable	N	
			Missing	Null	
		Negative	-	N	
		Missing	Missing	Quantifiable	Null
				Not Quantifiable	N
Missing	Null				
Missing	Positive	-	-	Null	
	Negative	Positive	Quantifiable	Y	
			Not Quantifiable	Null	
		Missing	Null		
		Negative	-	Null	
	Missing	-	Null		
	Missing	-	-	Null	

HCVAb	HCV RNA	Coinfection Status
Positive	Quantifiable	Y
	Not Quantifiable	N
	Missing	Null
Negative	-	N
Missing	Quantifiable	Null
	Not Quantifiable	N
	Missing	Null

“-” means any value can be present, as it does not affect the classification

- For incident coinfection, all laboratory tests must share the same accession number and if any set of values meets the criteria, then the subject is considered to have incident coinfection
 - The incident coinfection status will be one of two values: Yes/Null
 - The following tables provide combinations of HBV and HCV tests that are considered “Y” for incident coinfection status (all others are considered Null)

HBsAg	HBsAb	HBcAb	HBV DNA	Coinfection Status
Positive	-	-	-	Y
Negative	Negative	Positive	Quantifiable	Y
Missing	Negative	Positive	Quantifiable	Y

HCVAb	HCV RNA	Coinfection Status
Positive*	-	Y
-	Quantifiable	Y

* Subjects with positive HCVAb postbaseline must also have negative or missing HCVAb at baseline in order to be considered as having incident HIV/HCV coinfection.

“-” means any value can be present, as it does not affect the classification

- For adverse events, the start date must be after the first dose date of B/F/TAF (including both phases) and on or prior to the last dose date

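### For DTG-to-B/F/TAF switchers, the SAP sets baseline HBV status from on-treatment results, so some infections documented at screening are classed as not coinfected

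*SAP*

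**What the plan says.** **Reference date.** For switchers, Study Day 1 of the all B/F/TAF analysis is "the day when the first dose of B/F/TAF in the extension phase was taken" (SAP 3.8.1). SAP 1.2 puts this late: "Subjects will be treated for at least 144 weeks during the blinded treatment phase". The reset is deliberate, since switchers "will have a new baseline value for the All B/F/TAF analysis" (SAP 3.8.1). For the B/F/TAF arm, Study Day 1 is the first randomized dose.

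**Definition.** SAP 9.1 gives two routes to baseline HBV coinfection. The first reads "Positive HBsAg on or prior to the first dose date of B/F/TAF (including both phases), or". The second is HBsAg negative, HBsAb negative, HBcAb positive and HBV DNA of at least 20 IU/mL by the same date. Neither says which record to use when a test has several.

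**Record selection.** Item 19 of SAP Appendix 6 supplies that: "take the latest, non-missing record on or prior to the first dose date of B/F/TAF (including both phases) for each test". A status table then turns the four results into Y, N or Null.

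**Outputs.** The flag selects subjects for two listings in SAP 9.1 (AEs; liver-related tests with HBV DNA). It also fills a row of the baseline disease table, "HIV/HBV coinfection status (Yes/No/Missing, see Section 9.1 for definition" (SAP 5.2).

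**Testing.** Protocol 6.4 fixes the panel "For subjects who meet the definition of HBV infection at any visit": HBsAb, HBsAg and HBeAg at set weeks, plus HBV DNA. HBcAb is not in it. The End of Blinded Treatment Visit adds "Plasma HBV DNA (for subjects who meet the definition of HBV infection" (Protocol 6.5.2).

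**The concern.** One rule is applied to two kinds of record. The B/F/TAF arm is classified on samples taken before any study drug. Switchers are classified on samples taken after nearly three years of a regimen containing F/TAF. A switcher who met the SAP's own HBV criteria at screening can therefore be recorded as not coinfected because a marker changed on treatment.

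At stake are the HBV-specific descriptive outputs of the final analysis: who appears in the coinfection listings, how the two columns of the baseline HBV row compare, and whether an infection known since screening is reported as newly acquired. Few subjects are likely to qualify, so one or two misplaced subjects could change how those listings read.

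**Working it through.** The plan states no figure on this point, so there is nothing to reproduce. The check applies item 19's status table to profiles of infected subjects.

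**Inputs.** All four results exist at screening: Protocol 6.2.1 tests HBsAg, HBsAb and HBcAb, with reflex HBV DNA. HBV-infected subjects may enroll unless HBV DNA exceeds 9 log IU/mL (Protocol 4.3). At the switch, HBsAg, HBsAb and HBV DNA come from on-treatment samples. Because the scheduled panel for infected subjects omits HBcAb, its latest result is normally the one from screening.

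**Baseline status.** Results are in the order HBsAg / HBsAb / HBcAb / HBV DNA; Q = quantifiable, NQ = not quantifiable.

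| Profile | Screening records | Latest records at switch | Any-sample rule |
|---|---|---|---|
| 1. HBsAg stays positive, DNA suppressed | +/−/+/Q: Y | +/−/+/NQ: Y | Y |
| 2. HBsAg lost, no HBsAb, DNA unquantifiable | +/−/+/Q: Y | −/−/+/NQ: **N** | Y |
| 3. HBsAg lost, HBsAb gained | +/−/+/Q: Y | −/+/+/NQ: **N** | Y |
| 4. HBsAg lost, no HBsAb, DNA still quantifiable | +/−/+/Q: Y | −/−/+/Q: Y | Y |
| 5. Isolated HBcAb, DNA becomes unquantifiable | −/−/+/Q: Y | −/−/+/NQ: **N** | Y |
| 6. Isolated HBcAb, DNA still quantifiable | −/−/+/Q: Y | −/−/+/Q: Y | Y |

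Three of the six change from Y to N. Profile 1 does not, because the table's first row gives Y for a positive HBsAg whatever the other results.

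**Re-entry as incident.** A subject classed N can qualify later, but item 19 requires all tests to carry one accession number.

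- HBsAg returns: Y, so a documented infection is labelled incident.
- HBV DNA rebounds, HBsAg and HBsAb negative, HBcAb positive on the same accession: Y.
- HBV DNA rebounds with no HBcAb on that accession: Null.

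The third pattern is what the open-label schedule would normally produce. Protocol 6.5.3 repeats the panel without HBcAb every 24 weeks and HBV DNA every 12 weeks. The ALT-flare reflex tests in Protocol 7.5.4.1 also omit HBcAb. Unless a listed hepatitis B AE is reported while on B/F/TAF, such a rebound may not be flagged.

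**What stays visible.** SAP 7.1.6 lists all AEs. SAP 7.2 lists hematology, chemistry and urinalysis from both phases. SAP 7.2.4 lists subjects with AST or ALT above 3 × ULN. HBV DNA is named as listing content only in SAP 9.1.

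**Size.** Number affected = (switchers infected by the HBsAg route × share in profile 2 or 3) + (switchers infected by the HBcAb/DNA route × share in profile 5). The documents give none of these four quantities.

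**The case against.** The strongest reply is that the reset is intended and consistent. Switchers get a new baseline for everything, including HIV-1 RNA and CD4 in the same table, and SAP 9.1 ties baseline coinfection to the first B/F/TAF dose. On that view item 19 merely names the record, and asking for ever-infected status substitutes another quantity. The reset stands for measured values. It does not explain why an infection documented under the SAP's own criteria should be recorded as absent, or later as incident. SAP 9.1 never says latest, so body and appendix can be read differently. The protocol's any-visit wording helps less than it may seem: it governs which samples are drawn and is not an analysis definition.

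Three stronger readings are tempting, and the documents do not support them.

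- *Any HBV suppression on blinded drug removes the subject.* It does not: profile 1 stays Y. HBV DNA matters only once HBsAg is negative or missing.
- *These subjects vanish from HBV safety reporting.* AEs and liver chemistry remain in the general listings. A return of HBsAg or a listed hepatitis B AE on B/F/TAF brings the subject into incident listings with the same content.
- *The rule hides exacerbation after the extension.* Subjects move to commercially available treatment after Week 96 OL, and the documents do not say that HBV-active therapy then ends. The 30-Day Follow-Up schedules no HBV DNA (Protocol 6.6.2), and liver tests up to 30 days after last dose are already summarized (SAP 7.2.4).

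**Conclusion.** The point holds in a limited form. Item 19 classifies switchers on on-treatment records and the B/F/TAF arm on pre-treatment records. It returns N for switchers with HBsAg loss (with HBsAb seroconversion, or with HBV DNA not quantifiable) and for isolated-HBcAb switchers whose HBV DNA became unquantifiable, although the screening records return Y. Their HBV DNA then appears in no named listing unless they re-qualify as incident, in which case a known infection carries the wrong label.

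The number affected may be zero. Any count would need assumed rates of HBV prevalence, HBsAg loss and DNA suppression, and I offer none. That the study drugs lower HBV DNA is itself an inference: Protocol 1.7 foresees use in chronic hepatitis B and Protocol 7.5.4.2 manages exacerbation after stopping, but neither states it. The classification result does not depend on that inference; how often it occurs does. Only descriptive output is touched. The primary endpoint and every inference are unaffected, so this is a minor point.

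**What to change.** In SAP 9.1 and item 19, set baseline HBV status to Yes if the HBV criteria were met on any sample from screening through the first B/F/TAF dose: HBsAg positive at any visit, or the HBsAg-negative, HBsAb-negative, HBcAb-positive, HBV DNA quantifiable pattern on one sample. Exclude those subjects from incident HBV. Label the row in the SAP 5.2 table to match.

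The cost is a wording change in two places and a few lines of code on data already collected. There are two side effects. A few subjects with lasting HBsAg loss stay in the listing, where their results can be read directly. A B/F/TAF-arm subject with HBV DNA quantifiable at screening but not on Day 1 would also become Yes.
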